9.2.3. Descriptive Safety Outcomes

In addition, descriptive safety data will be reported on:

- Percentage of participants discontinued trial medication due to AE/SAE during the active run-in period

-
- All SAEs, by severity and by System Organ Class (SOC) criteria during the run-in period, by trial medication group during the randomized period, and safety follow-up period.

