2.4.2.2 Secondary

- Percentage of participants discontinued trial medication due to AE/SAE from randomization to follow-up Week 6.
- Percentage of participants with an SAE from randomization to follow-up Week 12.
- Percentage of participants with an SAE from randomization to follow-up Week 6.

- Percentage of participants with symptomatic hypotension from randomization to follow-up Week 12.
- Percentage of participants with symptomatic hypotension from randomization to follow-up Week 6.
- Percentage of participants with serum sodium concentration below 135 mmol/l at follow-up Week 12.
- Percentage of participants with serum sodium concentration below 135 mmol/l at follow-up Week 6.
- Percentage of participants with serum sodium concentration above 145 mmol/l at follow-up Week 12.
- Percentage of participants with serum sodium concentration above 145 mmol/l at follow-up Week 6.
- Percentage of participants with serum potassium concentration below 3.5 mmol/l at follow-up Week 12.
- Percentage of participants with serum potassium concentration below 3.5 mmol/l at follow-up Week 6.
- Percentage of participants with serum potassium concentration above 5.5 mmol/l at follow-up Week 12.
- Percentage of participants with serum potassium concentration above 5.5 mmol/l at follow-up Week 6.
- Percentage of participants with serum sodium <135mmol/l or >145 mmol/l, and/or serum potassium <3.5 mmol/l or >5.5mmol/l at follow-up Week 12.
- Percentage of participants with serum sodium <135mmol/l or >145 mmol/l, and/or serum potassium <3.5 mmol/l or >5.5mmol/l at follow-up Week 6.
- Percentage of participants with eGFR drop of over 30% from randomization to follow-up Week 12.
- Percentage of participants with eGFR drop of over 30% from randomization to follow-up Week 6.
- Percentage of participants with orthostatic hypotension at Week 6,
- Percentage of participants with orthostatic hypotension at Week 12
- Percentage of participants with orthostatic hypertension at Week 6,
- Percentage of participants with orthostatic hypertension at Week 12

In addition, descriptive safety data will be reported on:

- Percentage of participants discontinued trial medication due to AE/SAE during the active run-in period.
- All SAEs, by severity and by System Organ Class (SOC) criteria in the run-in period and by trial medication group in the randomized period and safety follow-up period.

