3.4.2 Safety Set

The Safety Set is defined as all participants who took at least one dose of study treatment, including during Period 1 single-blind run-in. For the analysis of the safety endpoints, participants will be analyzed in the treatment group they actually received.

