3.11.1.2 Adverse Event Summaries

For the summary of safety parameters, AEs will be classified according to the treatment period and treatment received as of the start date of the AE (Section 3.5.3). If an AE is ongoing at the time of randomization, it will be allocated to the Period 1 treatment. If a treatment ongoing at randomization worsens following randomization, the AE worsening will be allocated to the Period 2 treatment.

AESIs and SAEs will be classified according to the MedDRA (Medical Dictionary for Regulatory Activities) system (version 24.0, March 2021) and summarized by system organ class and preferred term.

Treatment periods for AE summary include: Period 1, Period 2, Period 3, Randomization Period, and Period 4. The total number of events and incidence of participants experiencing AESIs will be tabulated by treatment group and overall for the specified study periods.

For each period, any AESI or SAEs that emerges or worsens during the period of interest will be summarized:

- Adverse Events of Special Interest,
- Serious AE,
- Related AESIs defined as those judged by the investigator to be 'possibly', 'probably' or 'definitely' related
- Related SAEs defined as those judged by the investigator to be 'possibly', 'probably' or 'definitely' related,
- AE leading to trial medication discontinuation
- AE leading to trial discontinuation defined as a request by the participant to withdraw from future follow-up visits

AESIs of abnormality detected in laboratory assessments for Period 1 will only include those whose lab value for that parameter was in the normal range at baseline. Summaries of AESI and SAEs occurring during the Randomized Period will include risk differences with 95% CI, computed using the Newcombe hybrid score method (with continuity correction; https://pubmed.ncbi.nlm.nih.gov/21996567/), to evaluate GMRx2 against each dual control treatment group and overall. System organ classes and preferred terms with events occurring in at least 1% of the sample will be included.

In addition, the frequency and percentage of participants discontinuing treatment due to an AE will be reported with risk differences between treatment groups computed using the Newcombe hybrid score method (with continuity correction) to evaluate the primary safety endpoint among GMRx2 treatment participants compared to each dual control treatment group, and overall.

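### The 1% cut-off on SOC and preferred-term rows in SAP 3.11.1.2 has no stated scope or denominator and does not exempt SAEs, so it can remove an excess confined to GMRx2 from the between-arm comparison

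*SAP*

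**What the plan says.** SAP 3.11.1.2 makes four statements, in this order:

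- AESIs and SAEs are coded in MedDRA and "summarized by system organ class and preferred term". No threshold is given.
- "For each period, any AESI or SAEs that emerges or worsens during the period of interest will be summarized". Again no threshold is given.
- "Summaries of AESI and SAEs occurring during the Randomized Period will include risk differences with 95% CI", by the Newcombe hybrid score method with continuity correction, for GMRx2 against each dual and overall.
- Directly after that: "System organ classes and preferred terms with events occurring in at least 1% of the sample will be included".

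The descriptive safety outcome in SAP 2.4.2.2 is "All SAEs, by severity and by System Organ Class (SOC) criteria in the run-in period and by trial medication group" in the randomized and safety follow-up periods. Protocol 9.2.3 has the same outcome: "All SAEs, by severity and by System Organ Class (SOC) criteria during the run-in period, by trial medication group".

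The SAP does not define the sample in the 1% sentence. The Safety Set in SAP 3.4.2 is "all participants who took at least one dose of study treatment, including during Period 1 single-blind run-in". SAP 3.11.2 restricts the binary secondary safety endpoints to randomized participants; SAP 3.11.1.2 carries no such restriction.

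**The concern.** The sentence before the cut-off names SAEs, and the cut-off does not exempt them. A table of all SAEs by SOC and a table limited to terms reaching 1% cannot be the same table. The SAP does not say that they are two tables, so whoever programs the output must guess.

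The rule also appears to count over all arms together. Allocation is 2:1:1:1, so an event found in one arm only is diluted by the arms without it. Comparing the safety of GMRx2 with each dual is the trial's secondary objective (Protocol 6.2). At stake is whether a SOC or preferred term with a visible imbalance gets a row in the table meant to show it.

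**Working it through.** **Inputs.** Planned arms are 600 on GMRx2 and 300 on each dual, 1500 in all (Protocol 12.3). The final number randomized is given only as over 90% of plan (SAP Appendix 2). At least 2000 participants may enter run-in (Protocol 12.3). SAP 3.11.1.2 gives no figure to reproduce other than the 1%.

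**1. Largest count left out.** A row needs ceil(0.01 × N) participants, so the largest omitted count is one less.

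| Meaning of the sample | N | Needed | Largest omitted | As % of one dual arm | As % of GMRx2 |
|---|---|---|---|---|---|
| Planned randomized | 1500 | 15 | 14 | 14/300 = 4.7% | 14/600 = 2.3% |
| 1400 randomized | 1400 | 14 | 13 | 13/280 = 4.6% | 13/560 = 2.3% |
| Just over 90% of plan | 1351 | 14 | 13 | 13/270 = 4.8% | 13/540 = 2.4% |
| Safety Set with run-in | 2000 | 20 | 19 | 19/300 = 6.3% | 19/600 = 3.2% |

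The last row applies only if run-in failures count in the denominator of a Randomized Period table.

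**2. Imbalances that would be omitted at N = 1500.** The method is the SAP's own. The difference is d = p1 − p2, with lower limit d − √[(p1 − l1)² + (u2 − p2)²] and upper limit d + √[(u1 − p1)² + (p2 − l2)²]. Here l and u are Wilson limits with continuity correction.

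- *Excess confined to GMRx2.* For 14/600, p = 2.33% with limits 1.33% and 3.98%. For 0/300 the upper limit is 1.58%. The lower limit is 2.33 − √(1.00² + 1.58²) = 0.47 and the upper is 2.33 + √(1.65² + 0²) = 3.98. The result is **2.3% (0.5 to 4.0)**, Fisher p = 0.007, and it is the same against each of the three duals. The lower limit is above zero for GMRx2 counts of 11 to 14; at 10 it is −0.1%.
- *Excess confined to one dual.* 14/300 against 0/600 gives **4.7% (2.5 to 7.9)**, Fisher p = 1.7 × 10⁻⁷. This is the extreme ceiling.
- *Harm from one component.* Each drug is in three of the four arms, which is 600 + 300 + 300 = 1200 participants. At an equal rate in those arms, the term is omitted only up to 14/1200 = **1.17%**. That corresponds to 7/600 against 0/300 in the arm without the drug: 1.2% (−0.5 to 2.5).

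**3. How many SAE rows would fall below 15.** The documents give no expected SAE rate for this trial, so I assume 1% to 7.7%. The top of the range is the triple-pill arm of the earlier 6-month open-label trial (Protocol 5.4). For a SOC or term holding a share s of SAE participants at SAE rate r, the chance of reaching 15 is P(X ≥ 15), with X ~ Binomial(1500, r × s).

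| SAE rate | s = 10% | s = 20% | s = 30% |
|---|---|---|---|
| 1% | <0.0001 | <0.0001 | <0.0001 |
| 2% | <0.0001 | 0.001 | 0.04 |
| 3% | <0.0001 | 0.04 | 0.38 |
| 5% | 0.01 | 0.53 | 0.96 |
| 7.7% | 0.19 | 0.97 | >0.999 |

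A preferred term with a small share will almost always drop out at rates of 1% to 5%. A SOC that pools many terms may not.

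**The case against.** The strongest reply is that the cut-off is narrower than it looks. It follows the risk-difference sentence, and two earlier statements in the same section promise SOC, preferred-term and per-period summaries with no threshold. The outcome of all SAEs by SOC is listed as descriptive and promises no risk difference. Read by position, the rule decides only which rows carry an interval, and nothing is contradicted. This stands as a possible reading, but the SAP does not state it, and terms below the cut-off still lose their comparison. Table shells that were not available to me may settle the scope.

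Four stronger inferences are tempting, and the documents do not support them:

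- *That any harm tied to one drug would vanish.* Each component is in three of four arms, so such a harm at an equal rate is hidden only to about 1.2%, where the interval includes zero. The 14/300 case needs an event in one dual and none in the triple, which contains the same two drugs at the same doses.
- *That the SAE table by SOC would be close to empty.* This rests on an SAE rate and a spread over SOCs that the documents do not give.
- *That symptomatic hypotension is lost because it splits over several preferred terms.* SAP 2.4.2.2 defines it per participant: "Percentage of participants with symptomatic hypotension from randomization to follow-up Week 12". A display cut-off on terms does not filter that endpoint.
- *That the 6.3% and 3.2% ceilings are the likely ones.* They require run-in failures in the denominator, and SAP 3.11.2 excludes these for the binary secondary safety endpoints.

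**Conclusion.** The point holds as a gap in specification with a real but bounded consequence. SAP 3.11.1.2 sets an unqualified 1% rule without scope, denominator or an SAE exemption. Whether it contradicts the outcome of all SAEs by SOC depends on a reading that the SAP leaves open. On either reading, at N = 1500 with pooled counting, a SOC or preferred term seen in 11 to 14 GMRx2 participants and in no dual participant would go uncompared, although the SAP's own interval excludes zero.

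The size rests on three assumptions: the sample means all randomized participants pooled, arms are at planned size, and the event is confined to one arm. At just over 90% of plan the ceilings barely move (2.4% of GMRx2, 4.8% of one dual). The share of SAE rows lost cannot be fixed from the documents: most preferred terms at SAE rates of 1% to 5%, but not necessarily the larger SOCs.

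The overall SAE percentage, discontinuations due to AEs, and the sodium, potassium and eGFR outcomes are reported without the filter. The main safety conclusions are therefore not at risk. It should be corrected because the change is cheap and removes a rule that can hide an excess on the test product.

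**What to change.** Replace the sentence in SAP 3.11.1.2 with:

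> *SAEs: all SOCs and preferred terms are tabulated by treatment group with no frequency cut-off. AESIs: SOCs and preferred terms occurring in at least 1% of randomized, treated participants in any treatment group are included.*

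This settles the denominator and makes the SAE tables match SAP 2.4.2.2 and Protocol 9.2.3. For AESIs, 3 of 300 in a dual arm or 6 of 600 on GMRx2 would then be enough for a row, against 15 of 1500 pooled. One row per AESI category of Protocol 17.1.2, with the same risk difference, would help the reader but is optional.

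The cost is SAP and table-shell wording only, with no new data. The tables become longer, with more low-count rows and wide intervals. More rows also mean that some intervals will exclude zero by chance, so the comparisons should be labelled descriptive.

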3.11.2 Laboratory Parameters: Hematology, Biochemistry & Urine

Blood hematology, biochemistry and urine parameters will be collected according to the schedule of events. Only scheduled visit results will be presented in summary tabulations. Unscheduled visits will be included in data listings only. The baseline value for each parameter will be the latest non-missing value recorded before randomization (i.e., prior to Period 2).

Estimated Glomerular Filtration Rate (eGFR) results provided by the various pathology laboratories across study may be calculated by different equations; however any differences are expected to be balanced across randomized treatment groups and no adjustments will be made.

Actual values and changes from baseline for all laboratory parameters will be descriptively summarized by

treatment group. A subset by-participant listing of out-of-range values will be presented.

In addition, tabular descriptive summaries will present the number and percentage of participants at Week 6 and 12 with:

- serum sodium concentration below 135 mmol/l
- serum sodium concentration above 145 mmol/l
- serum potassium concentration below 3.5 mmol/l
- serum potassium concentration above 5.5 mmol/l
- serum sodium <135mmol/l or >145 mmol/l, and/or serum potassium <3.5 mmol/l or >5.5mmol/l at week 6
- serum sodium <135mmol/l or >145 mmol/l, and/or serum potassium <3.5 mmol/l or >5.5mmol/l at week 12
- eGFR (estimated GFR) drop of over 30% from baseline

Frequencies and proportions, including frequency of missing data will be presented. Risk differences with 95% CI, computed using the Newcombe hybrid score method (with continuity correction), to evaluate GMRx2 against each dual control treatment group will be performed. The analysis of binary secondary safety endpoints will be performed on the Safety Analysis Set, limited to those participants who were randomized. Participants will be grouped as treated.

3.11.3 Other Safety Analysis

Weight and BMI will be summarized descriptively using at actual values and changes from baseline by treatment groups.

Appendix 1: List of Abbreviations

Abbreviation	Definition
AE	Adverse Event
AESI	Adverse Event of Special Interest
ATC	Anatomical Therapeutic Chemical
ВР	Blood Pressure
СІ	Confidence Interval
cm	Centimeters
CRO	Contract Research Organization
DBP	Diastolic Blood Pressure
ECG	Electrocardiogram
eGFR	estimated Glomerular Filtration Rate
EOT	End of Trial
EU	European Union
FAS	Full Analysis Set
FCS	Fully Conditional Specification
FDA	USA Food & Drug Administration
GEE	Generalized Estimating Equation
GM	George Medicines
GMRx2	Single pill combinations of telmisartan/amlodipine/indapamide
ICH	The International Conference
LOCF	Last Observation Carried Forward
LS	Least Square
MedDRA	Medical Dictionary for Regulatory Activities
MI	Multiple Imputation
mg	Milligram
mmHg	Millimeters of Mercury
MMRM	Mixed Model with Repeated Measures
(Q1-Q3)	Interquartile limits
RCT	Randomized Controlled Trial
RR	Risk ratio
SAE	Serious Adverse Event
SAP	Statistical Analysis Plan
SAS	Statistical Analysis Software
SBP	Systolic Blood Pressure
SD	Standard deviation
SOC	System Organ Class
STEAE	Serious Treatment-Emergent Adverse Event
TE	Treatment-Emergent
USA	United States of America
WHO	World Health Organization

Appendix 2: Additional Power Calculations

As noted in Section 2.5, the initial power calculation presented is a very conservative calculation, which is based on a simple comparison of mean values and a common standard deviation of the actual SBP values i.e., T-test of sample means with equal variances. Our modelling approach – a multivariable mixed model – is similar to an ANCOVA (Analysis of Covariance) type of analysis which will explicitly consider an adjustment for the baseline SBP values. A sample size calculation based on the ANCOVA (which would be more powerful than the simple and more conservative t-test approach used above) and on the same assumption as before (allocation ratio of 2:1 of GMRx2 vs dual, alpha 0.05, equal SD across arms of 11) would lead to the following power: 98% if regressing the SBP values to the specific covariate set the R² (proportion of variance explained) achieved is 10%, 99% if R² is 20%, 99.6% if R² is 30% with overall power respectively 95%, 97% and 99%. These R² values were considered to be conservative, since two similar, completed BP trials (TRIUMPH and QUARTET) each had R² values over 40% in mixed models on SBP data using treatment, time, their interaction and SBP at baseline and compared with the null model.

Supply chain and logistics issues, substantial recruitment delays related to the COVID-19 pandemic and other unanticipated issues caused unplanned and significant trial conduct interruptions. As a result of these delays, a re-supply of IMP became infeasible. In addition, there had been independent review of study power at two Steering Committee meetings (6 Dec 2022 and 14 Feb 2023), based on the prespecified statistical approach of a mixed model repeated measures and blinded standard deviation of the overall sample, that the trial likely would have more statistical power than the univariate approach on which initial powering was modelled, as detailed above. These estimates were made without any reference to unblinded data. The Sponsor informed the Steering Committee of the pending IMP supply situation at their meeting on 11 April 2023, and given these challenges and blinded study power assessment that indicated the trial already had as much power as originally planned, the Steering Committees, the Steering Committee Chair wrote to the Sponsor on 21 April 2023 recommending a premature termination of recruitment. Based on the foregoing, the Company decided to terminate recruitment to the study. The final number of patients randomized was over 90% of the planned sample size.

Appendix 3: Schedule of Assessment

Visit Name	SCREEN ¹⁰	Run-in start ¹¹	Pre- RAND	RAND (Run-in end)	FU1 (Forced up- titration)	FU2 (End of trial medication)	EOT (Telephonic safety FU)
Visit Week	Week -4	Week -4	Week - 4 to -1		Week 6	Week 12	Week 16
Visit Day	-28	-28	During	0	42	84	112
(Visit window days)	(±7)	(±7)	Run-in		(±7)	(±7)	(±7)
Eligibility (inclusion & ovelusion)	•						
Medical history	• •			•			
Physical examination ²	· ·						
	· · ·						
Height							
Weight						✓	
Clinic BP, standing BP, pulse	· · · · · · · · · · · · · · · · · · ·			 ✓ 	 ✓ 	· ✓	
12-lead electrocardiogram (ECG)	· ·			-	-	-	
Dispense home BP monitor [*]		✓					
Home BP monitoring							
Home BP monitor brought to						./	
clinic				•	•	•	
Blood Collection*							
Results needed before run-in ³							
creatinine, liver function	~						
Pregnancy test if childbearing potential [†]	~						
Results needed before randomization ⁴							
Fasting glucose			✓			✓	
HbA1c⁵			✓				
Fasting lipid profile ⁶			✓			✓	
Complete blood count ⁷			✓				
Liver function test ⁸			✓			✓	
Sodium, potassium, chloride			✓		✓	✓	
Calcium			✓			✓	
Creatinine with eGFR ⁹			✓		✓	✓	
Uric acid			✓			✓	
Thyroid-stimulating hormone			✓				
Other tests							
Blood sample for storage for substudy						~	
Urine Collection*							
Albumin-creatinine ratio ⁴			~			✓	
Medications							
Discontinue non-trial BP lowering medications		✓					
Allocation of randomized trial medication				~			
Dispensation of trial medication*		✓		✓	✓		

Return of trial medication				✓	✓	✓	
Adherence to trial medication				✓	✓	✓	
Review of concomitant medications	~			~	✓	~	~
Safety							
AESI or SAE							

¹ At Screening visit, if not collected previously. Written informed consent may be collected pre-screening.

² Systems-based examination deemed necessary for the safety of participants by the site investigator

³ Results must be reviewed for eligibility prior to beginning run-in. If blood tests have been conducted within the past 3 months, these results can be utilized to assess suitability for run-in. If preferred locally, tests can be arranged prior to screening visit, once informed consent is obtained.

⁴ Results must be reviewed for eligibility prior to randomization. Tests can be conducted during run-in ⁵For participants with diabetes without a HBA1c in past 3 months, HBA1c can be taken at screening to determine eligibility for randomization at randomization visit:

⁶ Total cholesterol, low-density lipoprotein cholesterol, high-density lipoprotein cholesterol

⁷ Red blood cell count, hemoglobin, hematocrit, mean corpuscular volume, reticulocyte count, white blood cell count, platelet count

⁸ Bilirubin, albumin, total protein, gamma-glutamyl transferase, alkaline phosphatase, aspartate transaminase and alanine transaminase

⁹ recent eGFR must be known prior to run-in start. If not available in last 3 months, the start of run-in should be delayed until results available from measure taken at the time of screening/run-in blood tests

¹⁰⁻Screening visit to take place 0-14 days prior to run-in start

¹¹ Option to extend run-in from 28 to up to 35 days (i.e. by up to 1 week) if there have been technical issues with BP machine use and or measurement protocol

* All laboratory investigations and ECG will be performed at the trial site or local laboratory.

* Serum pregnancy test for women of child-bearing potential. In some jurisdictions, including Czech Republic, Poland and South Korea, women of childbearing potential will be required to undergo pregnancy testing and the result followed-up every 4 weeks after starting trial medication until Week 12, end of randomized treatment period.

If respective blood test results are not available by the screening and randomization visits, once eligibility has been confirmed, participants may need to return to the clinic to collect the trial medication and home BP monitor. Alternatively, where feasible, and consent from the participant received, they may be couriered to the participant's home.

EOT=End of trial; FU=Follow up; PRESCREEN=Pre-screening; RAND=Randomization; SCREEN=Screening

